## 8 STATISTICAL METHODS OF ANALYSIS

### 8.1 General Principles

The statistical analyses will be reported using summary tables, figures, and data listings. Statistical tests will be 2-sided at the alpha=0.05 significance level and 2-sided 95% confidence interval will be used. All p-values will be presented as nominal p-values. No adjustment on multiplicity will be made. Continuous variables will be summarized with means, standard deviations, standard errors, medians, Q1, Q3, minimums, and maximums. Categorical variables will be summarized by counts and by percentages of subjects in corresponding categories. No imputation on missing data will be made, unless stated otherwise. All data obtained from the CRFs as well as any derived data will be included in data listings.

The Week 24 analysis will be performed when all patients enrolled in the study have completed the Week 24 visit or have discontinued the study. The final analysis will be conducted when all patients enrolled in the study have completed the Week 72 visit or have discontinued the study.

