#### 8.1.1 Repeated Measure Model: General Estimating Equations

When the sample size and number of observations allow it, the change from baseline over time and the binary endpoints over time will be analyzed using a generalized estimation equation (GEE) model that includes time as the categorical variable and adjusted for baseline measurement. The covariance structure that will be used for the GEE model is compound symmetry which specifies constant variance for the assessments and constant covariance between the assessments over time. If the compound symmetry covariance structure leads to non-convergence, Quasi-Likelihood Information Criterion (QIC) will be used to select the best covariance structure. Model based estimates of the changes from baseline and corresponding 95% confidence intervals will also be provided along with p-values for assessing statistical significance.

The p-value for testing the statistical significance of the change from the baseline to week 24 (for the interim analysis) and to week 72 (for the final analysis) assessments will be provided for changes from baseline in primary PD endpoints, selected safety endpoints (eGFR, creatinine, amylase), PRO endpoints (BPI, WOMAC, SF-36) and clinical outcomes endpoints (6MWT, percent predicted 6MWT, TUG).

For week 24 analysis, only measurements up to week 24 will be included in the model. For final analysis (week 72), all measurements will be included in the model.

If the number of observations are insufficient for analyses using a GEE model, a descriptive summary will be provided, and analyses using observations at a single time point, such as paired t-test or nonparametric methodologies, will be considered.

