## 8.8 Endpoints

### 8.8.1 Pharmacodynamic Endpoints

The number and proportion of subjects with serum phosphorus level in the normal range ( $\geq 2.5$  and  $< 4.5$ ) at each time point will be provided, along with the two-sided 95% confidence intervals, obtained using the GEE model described in Section 8.1.1. An overall summary of the number and proportion of patients who ever reached the normal range over the duration of the study will also be provided. Additional analyses of serum phosphorus including observed values, change from baseline, percent change from baseline over time will be summarized.

For the final analysis, the primary PD endpoints at all post-baseline visits will be compared to baseline using the GEE model described in Section 8.1.1, and the primary statistical comparison will be between the levels at baseline and week 72.

For the interim analysis, the primary PD endpoints at all post-baseline visits prior or at week 24 for all patients will be compared to baseline using the GEE model, and the primary statistical comparison will be between the levels at baseline and week 24.

For all primary PD endpoints descriptive statistics of observed values and of changes from baseline at each visit will be provided.

Graphs showing the change over time in key PD parameter for both observed measure and the change from baseline will be provided. The relationship between various PD parameters as well as KRN23 concentrations may be examined.

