### 8.8.2 Efficacy Endpoints

#### 8.8.2.1 PRO Endpoints

BPI (Worst Pain, Pain Severity and Pain Interference), WOMAC (the three domains) and SF-36 (the eight domains and the two components) scores and the proportion of responders at each study time point will be evaluated using descriptive statistics. The binary endpoints (responder/non-responder to treatment) and the changes from baseline to week 24 (interim analysis) and week 72 (final analysis) will be analyzed using the GEE model described in Section 8.1.1. Listings containing the answers to each question and each of the scores over time will also be provided. In addition, the cumulative distribution functions (CDF) based on change from baseline and percent change from baseline of worst Pain score will be provided.

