## 10 APPENDICES

### Appendix 1: UX023-CL203 Efficacy Endpoint Summary Table

Test / Instrument	Eligible Study Population	Endpoint	Pharmacodynamics, efficacy or safety endpoint	Timepoints for Assessment	Statistical approach at week 24 analysis	Statistical approach at week 72 analysis
PD	PD Analysis Set	Change from baseline in serum phosphorus	Pharmacodynamics	Baseline, Weeks 2, 4, 6, 8, 10, 12, 24, 26, 28, 36, 38, 40 48, 50, 52, 60, 72/ET	GEE Model	GEE Model
PD	PD Analysis Set	Percent change from baseline in serum phosphorus	Pharmacodynamics	Baseline, Weeks 2, 4, 6, 8, 10, 12, 24, 26, 28, 36, 38, 40 48, 50, 52, 60, 72/ET	GEE Model	GEE Model
PD	PD Analysis Set	Proportion of subjects with serum phosphorus level in the normal range	Pharmacodynamics	Baseline, Weeks 2, 4, 6, 8, 10, 12, 24, 26, 28, 36, 38, 40 48, 50, 52, 60, 72/ET	GEE Model	GEE Model
PD	PD Analysis Set	Change from baseline in iPTH	Pharmacodynamics	Baseline, Weeks 12, 24, 36, 48, 72	GEE Model	GEE Model
PD	PD Analysis Set	Change from baseline in Total FGF23	Pharmacodynamics	Baseline, Weeks 4, 8, 12, 24, 28, 36, 40, 48, 72	GEE Model	GEE Model
PD	PD Analysis Set	Change from baseline in Free FGF23	Pharmacodynamics	Baseline, Weeks 4, 8, 12, 24, 28, 36, 40, 48, 72	GEE Model	GEE Model
PD	PD Analysis Set	Change from baseline in 1,25(OH) 2 D	Pharmacodynamics	Baseline, Weeks 12, 24, 36, 48, 72	GEE Model	GEE Model

Test / Instrument	Eligible Study Population	Endpoint	Pharmacodynamics, efficacy or safety endpoint	Timepoints for Assessment	Statistical approach at week 24 analysis	Statistical approach at week 72 analysis
PD	PD Analysis Set	Change from baseline in 2-hr urine parameters (TmP/GFR, calcium, creatinine, calcium/creatinine ratio, phosphorus)	Pharmacodynamics	Baseline, Weeks 12, 24, 36, 48, 72	GEE Model	GEE Model
PD	PD Analysis Set	Change from baseline in 24-hr urine parameters (calcium, calcium/creatinine ratio, creatinine, phosphorus, phosphorus/creatinine ratio)	Pharmacodynamics	Baseline, Weeks 12, 24, 36, 48, 72/ET	GEE Model	GEE Model
PD	PD Analysis Set	Change from baseline in fractional excretion of phosphorus	Pharmacodynamics	Baseline, Weeks 12, 24, 36, 48, 72/ET	GEE Model	GEE Model
PD	PD Analysis Set	Change from baseline in bone biomarkers (ALP, BALP, CTx, P1NP)	Pharmacodynamics	Baseline, Weeks 24, 48, 72/ET	Paired t-test	GEE Model

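### The GEE that the SAP assigns to the normal-range proportion contains no Week 72 versus baseline contrast, so it cannot deliver the comparison promised for that endpoint

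*SAP*

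**What the plan says.** SAP 4.2 lists the primary pharmacodynamic endpoints. The first is the number and percentage of subjects with serum phosphorus in the normal range; the others are worded as changes from baseline.

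SAP 8.8.1 states that in the final analysis "the primary PD endpoints at all post-baseline visits will be compared to baseline using the GEE model described in Section 8.1.1", and names baseline against Week 72 as the primary statistical comparison. The interim analysis does the same with Week 24. SAP Appendix 1 has a row for "Proportion of subjects with serum phosphorus level in the normal range" and assigns it the GEE at both analyses.

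SAP 8.1.1 gives one model for both kinds of outcome: "the change from baseline over time and the binary endpoints over time will be analyzed using a generalized estimation equation (GEE) model". It is described as a "model that includes time as the categorical variable and adjusted for baseline measurement". On the working correlation it says: "The covariance structure that will be used for the GEE model is compound symmetry". The section describes its p-values as tests of the change from baseline to Week 24 or Week 72. It names no link function, no contrast and no form for the baseline term (phosphorus in mg/dL, or in range yes/no), and it does not make baseline a level of time in the response.

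**The concern.** For a continuous endpoint the outcome is the change itself, so a fitted mean of zero at Week 72 means no change and the test against zero is the right one. For the binary endpoint the outcome is status at each visit. Baseline enters only on the right-hand side, so the model describes the proportion in range after dosing, given baseline, and holds nothing to compare that proportion with.

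The SAP nevertheless promises a baseline comparison from this model for an endpoint tied to a stated primary objective. Whatever p-value the software prints at Week 72 could be reported as a change from baseline when it tests something else. It could then miss a real gain, or call an unchanged proportion significant.

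**Working it through.** **Inputs.** Two-sided alpha 0.05 (SAP 8.1). N is 20 in the protocol synopsis and about 25 in SAP 3.5. The documents give no expected in-range rate, power or effect size for this endpoint, so there is no planned figure to reproduce and every rate below is an assumption. SAP 5.1 puts at least 21 months between the last earlier dose and the first dose here, which makes a low baseline proportion plausible but does not give one.

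**Step 1: what the model can test.** Its parameters are one term per post-baseline visit and one baseline coefficient. None is the baseline proportion, so no combination of them equals Week 72 minus baseline. Appendix 1 lists Baseline among the time points for this row, but it does so for the change-from-baseline rows too, so the listing does not show that baseline is a response level.

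**Step 2: what a default analysis would test.** With x of n in range at Week 72, p̂ = x/n, and covariate and repeated visits ignored:

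- Logit link, fitted logit against 0 (null 50%): z = logit(p̂) × √(n p̂(1−p̂)).
- Identity link, fitted proportion against 0 (null 0%): z = p̂ / √(p̂(1−p̂)/n).
- Paired comparison: exact McNemar on the discordant pairs, assuming that subjects in range at baseline stay in range.

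Example, 1/20 rising to 10/20. Logit: logit(0.5) = 0, so z = 0 and p = 1.00. Identity: 0.5/√(0.25/20) = 4.47, p = 0.000008. McNemar: 9 discordant pairs, all one way, p = 2 × 0.5⁹ = 0.0039.

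| Baseline → Week 72 | Logit (null 50%) | Identity (null 0%) | Exact McNemar |
|---|---|---|---|
| 0/20 → 5/20 | 0.033 | 0.0098 | 0.0625 |
| 0/20 → 10/20 | 1.00 | 0.000008 | 0.0020 |
| 1/20 → 10/20 | 1.00 | 0.000008 | 0.0039 |
| 2/20 → 10/20 | 1.00 | 0.000008 | 0.0078 |
| 0/20 → 14/20 | 0.083 | <0.0001 | 0.00012 |
| 16/20 → 16/20, same subjects | 0.013 | <0.0001 | 1.00 |
| 0/25 → 12/25 | 0.84 | 0.0000016 | 0.0005 |

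The first two p-value columns do not depend on the baseline count. The 5/20 row is significant under the logit only because 25% lies below 50%.

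**Step 3: no true change.** At n=20 the logit test gives p<0.05 for x = 1 to 5 and 15 to 19 (x=5: |z| = 1.0986 × √3.75 = 2.13; x=6: 0.8473 × √4.2 = 1.74). The binomial probability of that set is 0.87, 0.89 and 0.79 for unchanged true rates of 10%, 15% and 20%.

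**Step 4: the model with covariate and repeated visits.** The closed form leaves both out, so the binomial-logit GEE was simulated: exchangeable correlation, categorical week, centred baseline phosphorus, 17 post-baseline visits, N=20, 400 runs per scenario, phosphorus means and SDs assumed (between-subject SD 0.3, within-subject 0.25 mg/dL). The table gives the share of runs with p<0.05 at Week 72.

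| Scenario | GEE Week 72 term | Exact McNemar |
|---|---|---|
| about 3% → about 50% | 10% | 94.5% |
| about 4% → about 79% | 83.6% | 100% |
| no change, about 20% | 83.5% | 0.3% |
| no change, about 50% | 6.5% | 1.2% |
| no change, about 80% | 85.3% | 0.9% |

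Runs without a finite p-value were dropped, leaving 359, 375 and 347 runs in the 79%, 20% and 80% scenarios; the cause was not examined. The simulation agrees with the closed form.

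**The case against.** **The 50% null is not in the SAP.** A reader might infer that the SAP tests the proportion against 50%. The documents do not support that: no link or tested parameter is stated, and Section 8.1.1 describes its p-values as tests of change from baseline. The 50% null follows from a default logit analysis, the 0% null from an identity link, and baseline as a time level would give a genuine baseline test. This stands. The finding is that the specified model lacks the promised contrast, not that a particular wrong null was chosen.

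**The p-value may never be printed.** The part of 8.8.1 specific to the proportion promises counts, proportions and 95% confidence intervals. SAP 4.2 words the endpoint as being in range at any time after dosing, and Protocol 7.6.2.5 plans only number and percent. This has weight, but the next paragraph of 8.8.1 covers the primary PD endpoints without excepting this one, and Appendix 1 assigns it the GEE.

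**The fallback could cover it.** Section 8.1.1 uses GEE only where the data allow, and would consider nonparametric methods otherwise. That is triggered by too few observations, not by a missing contrast, and commits to nothing.

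**PRO responders.** A reader might extend the fault to them because SAP 8.8.2.1 uses the same model. The documents do not support that. Section 8.1.1 promises p-values for changes in PRO scores and does not name responder status, and WOMAC response is itself defined as a change from baseline (SAP 5.4.1), so no baseline proportion is missing.

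**Consequence.** SAP 8.1 says: "All p-values will be presented as nominal p-values. No adjustment on multiplicity will be made". The study is exploratory and unpowered, and no decision rule rests on this p-value. A false signal at 15% in range would sit beside a printed 15% and could hardly pass as a gain. This stands and limits the severity.

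**Conclusion.** The point holds for one endpoint. The model in SAP 8.1.1 cannot produce the baseline versus Week 72 (or Week 24) comparison that 8.8.1 promises for the normal-range proportion, and nothing else in the documents supplies it. Two programmers following the text could report p=1.00 or p=0.000008 for the same 10/20.

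That conclusion rests on the wording alone. Its size rests on assumptions: n=20, a logit link, a Wald test of the Week 72 term, and in-range rates that the documents do not give. Under these, 1/20 rising to 10/20 is missed entirely, and an unchanged rate of 10% to 20% is called significant with probability 0.79 to 0.89. Where the Week 72 proportion is well above 50%, the default test will often agree with the paired test, but for the wrong reason.

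Continuous change-from-baseline endpoints and the descriptive proportions are unaffected, and this point does not concern the per-visit confidence intervals. With nominal p-values in an unpowered study, this should be fixed but does not undermine the trial.

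**What to change.** - In SAP 8.1.1, 8.8.1 and Appendix 1, for the normal-range endpoint, cross-tabulate in-range status at baseline and Week 72 (Week 24 at the interim), use the exact McNemar test, and report the paired difference with a 95% CI.
- If a GEE is kept for the time course, state the link, make baseline a level of time in the response and drop the baseline covariate. Keep the exact test as the primary comparison, because the logit contrast is not estimable if nobody is in range at baseline.
- For PRO responders, add only a sentence that no p-value from the fitted logit is reported as a change from baseline.
- Use one definition of the range in the cross-tabulation: SAP 4.2 includes 4.5 mg/dL and SAP 8.8.1 excludes it.

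The cost is SAP wording and one short program. No new data are needed.

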### 8.8.2 Efficacy Endpoints

#### 8.8.2.1 PRO Endpoints

BPI (Worst Pain, Pain Severity and Pain Interference), WOMAC (the three domains) and SF-36 (the eight domains and the two components) scores and the proportion of responders at each study time point will be evaluated using descriptive statistics. The binary endpoints (responder/non-responder to treatment) and the changes from baseline to week 24 (interim analysis) and week 72 (final analysis) will be analyzed using the GEE model described in Section 8.1.1. Listings containing the answers to each question and each of the scores over time will also be provided. In addition, the cumulative distribution functions (CDF) based on change from baseline and percent change from baseline of worst Pain score will be provided.

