**Table 1: WOMAC Scales, Number of Questions in Each Scale, and Scores from a General Population**

Scale Name	Number of WOMAC questions combined into scale score	Normative values from general population 	
		Mean*	Standard Deviation*
Pain	5	14.1	19.7
Stiffness	2	20.1	23.6
Physical Functioning	17	15.4	20.2

\* The published values are on a 0-10 scale and were converted here to a 0-100 scale by multiplying by 10.

All questions are measured on a 5-point Likert scale: none (0), mild (1), moderate (2), severe (3), and extreme (4). Scoring is a simple sum, so Pain scores could range from 0 to 20, Stiffness from 0 to 8, and Physical Functioning from 0 to 68, with higher numbers indicating worse condition. Scores are then normalized to a 0-100 metric representing the percent of the maximum score, where 0 was the best health state and 100 the worst.

WOMAC scores are not norm-based, so they cannot be interpreted directly as difference from a population mean. However, mean WOMAC scores from a large population-based sample of healthy adults have been published (Bellamy et al. 2011), giving benchmark values for comparison (Table 1).

[Appendix 3](#) includes the complete text of the WOMAC as it appears to subjects in the study.

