#### 5.4.1. MPCl for WOMAC Scales and Responder definition

The minimum perceptible clinical improvement (MPCl) for WOMAC scales are defined according to the WOMAC User Guide (Bellamy 2012) as follows:

- WOMAC Pain: 9.7 nu (normalized units)
- WOMAC Stiffness: 10.0 nu
- WOMAC Physical Functioning: 9.3 nu

For each of the three WOMAC scales the responders are the subjects with the decrease from baseline greater than or equal to the corresponding MPCl.

## 5.5 SF-36 Health Survey version 2

The SF-36v2 is a self-reported survey of general HRQL with a 4-week recall period. Its 36 questions measure eight underlying health domains, and responses to sets of questions are combined and scored to yield scale scores for each domain, as shown in Table 2.

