**Figure 1: Process for scoring SF-36v2 Health Domain Scales and Component Summary Measures**

### 5.5.1 MIC for SF-36v2 Scales and Responder definition

The Minimally Important Change (MIC) is the smallest change over time in an individual patient's score that represents a clinically significant change in their health status. Using a distributional approach with a US general population sample, MICs have been established for the SF-36v2 as: PF, 3.5 points; Role-Physical, 3.2; Bodily Pain, 4.5; General Health, 5.7; Vitality, 5.5; Social Functioning, 5.0; Role-Emotional, 3.8; Mental Health, 5.5; PCS, 3.1; and MCS, 3.8.

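### PRO responder rates count improvement only, in a study with no control group: chance alone gives a positive rate, and no planned WOMAC or SF-36 summary shows how many subjects worsened by the same amount

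*SAP*

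**What the plan says.** SAP 5.4.1 defines a WOMAC responder on each scale as a subject whose score falls from baseline by at least the threshold: 9.7 normalized units for Pain, 9.3 for Physical Functioning and, for the third scale, "WOMAC Stiffness: 10.0 nu". SAP 5.4 sums items scored 0 to 4, so the raw Stiffness score runs "Stiffness from 0 to 8" before rescaling to 0-100.

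SAP 5.5.1 lists a threshold for each SF-36 domain and both component scores (for example "PCS, 3.1; and MCS, 3.8") under a heading that promises a responder definition, but never writes the rule. SAP 5.3 gives no responder threshold for the BPI.

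SAP 8.8.2.1 reports the proportion of responders at each time point and sends "The binary endpoints (responder/non-responder to treatment" to the model in SAP 8.1.1. There, "the change from baseline over time and the binary endpoints over time will be analyzed using a generalized estimation equation (GEE) model" with categorical time and adjustment for baseline. No link function and no reference responder rate are given. The p-values that 8.1.1 goes on to list "will be provided for changes from baseline in primary PD endpoints", selected safety variables, the PROs and the functional tests; responder rates are not named. SAP 8.1 adds that "Statistical tests will be 2-sided at the alpha=0.05 significance level" and "All p-values will be presented as nominal p-values".

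The only planned display of a full distribution of change is the CDF for BPI worst pain (SAP 8.8.2.1). Protocol 7.2 confirms that there is no control group and that efficacy is exploratory.

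**The concern.** In a controlled trial, a one-sided responder rate is read against the rate in the other arm. Here nothing stands in that place. Everyone is a non-responder at baseline by construction, so the baseline rate is 0% and any later rate exceeds it. Subjects whose scores merely fluctuate will cross the threshold in both directions, and only the favourable crossings are counted.

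A reader shown a responder rate of, say, 30% therefore cannot tell whether it reflects benefit or noise. The figure that would help, the share who worsened by the same amount, is not in any planned WOMAC or SF-36 summary, although these are the only PROs with thresholds. SAP 3.6 says that the Week 24 output may support regulatory filings, where such a rate is easily over-read.

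**Working it through.** The plan states no responder rate, power or reference value, so there is no figure of its own to reproduce.

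**1. Scale steps.** One raw point is worth 100/(4 × items) normalized units.
- Stiffness, 2 items: 100/8 = 12.5. The threshold of 10.0 is below this, so one point is a response.
- Pain, 5 items: 100/20 = 5.0. The threshold of 9.7 needs two points (10.0).
- Physical Functioning, 17 items: 100/68 = 1.47. The threshold of 9.3 needs seven points (10.3).

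The item-imputation rule in SAP 7.2 does not alter the Stiffness result: a missing item takes the value of the other one, so the sum is still a whole number of points.

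**2. Chance responder rate.** With no true change, equal SD at both visits and retest correlation r, the change has SD = SD₀ × √(2(1−r)), and the rate is 1 − Φ(threshold / (SD₀ × √(2(1−r)))). SD₀ is 19.7, 23.6 and 20.2 for WOMAC Pain, Stiffness and Physical Functioning (SAP Table 1) and 10 for SF-36 (SAP 5.5). The correlation is not in the documents and is varied. Example at r = 0.8, where √(2 × 0.2) = 0.632: PCS 3.1/6.32 = 0.490, giving 31%; WOMAC Pain 9.7/(19.7 × 0.632) = 0.778, giving 22%.

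| r (assumed) | PCS | WOMAC Pain | Stiffness | Physical Functioning | Range, 13 scales |
|---|---|---|---|---|---|
| 0.5 | 38% | 31% | 34% | 32% | 28-38% |
| 0.7 | 35% | 26% | 29% | 28% | 23-35% |
| 0.8 | 31% | 22% | 25% | 23% | 18-31% |
| 0.9 | 24% | 14% | 17% | 15% | 10-24% |
| 0.95 | 16% | 6% | 9% | 7% | 4-16% |

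**3. Real WOMAC steps and floor.** Simulating whole-point scores bounded at 0-100, with Table 1 means and SDs and a latent correlation of 0.7 to 0.8, gives 21-17% for Physical Functioning, 25-21% for Pain and 32-29% for Stiffness. So the floor lowers Physical Functioning, while the coarse steps raise Stiffness (still 18% at 0.95). With an assumed mid-scale baseline of 40-50 and r = 0.8, Stiffness is about 33%. In each case the share worsening by the same amount matches the share improving.

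**4. Candidate reference rates, n = 20 (Protocol 7.6.4).**
- Against 0% at baseline, one responder already exceeds the reference. The probability of at least one by chance is 1 − 0.80^20 = 98.9% at a chance rate of 20%, and 1 − 0.67^20 = 99.97% at 33%.
- Against 50%, the point where a logistic visit mean is zero on the logit scale, a chance-only simulation of PCS (r = 0.8, five visits, exchangeable correlation, 400 runs) had a mean responder rate of 32%. It rejected 50% at Week 72 in 39% of runs, almost all because the rate was too low.

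Neither reference asks whether response exceeds chance.

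**5. Precision.** Exact 95% intervals at n = 20 are 9-49% for 5/20 and 15-59% for 7/20. As a hypothetical case, 7 improved and 5 worsened give a net difference of 2/20 = 10 points. Its approximate SE is √(12/20 − 0.10²)/√20 = 0.172, so the interval runs from −24 to +44 points. The one-sided figure of 35% would hide this.

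**The case against.** A reader might infer that the SAP will publish a GEE p-value testing responder rates against 50%, and so mark low rates as significant. The documents do not support that. SAP 8.1.1 ties its p-values to changes from baseline, the PRO rows of Appendix 1 list only changes from baseline, and SAP 8.8.1 uses the same model for its own binary endpoint to give proportions with 95% confidence intervals. Read that way, the responder GEE estimates visit rates and needs no null. The 50% reference would be a software default, not a stated plan. What stands is that no reference rate is named and no sentence rules a test out.

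A reader might also take a fifth to a third of subjects as an established chance rate. That holds only for correlations near 0.7 to 0.8 with general-population SDs; neither value is known for these subjects.

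It is fair, too, that worsening is not wholly invisible. The BPI worst-pain CDF, the quartiles and extremes in the summaries and the subject listings all carry some of it, and the mean-change GEE tests net direction. But none of these summaries gives the worsened share at the responder threshold for WOMAC or SF-36. Finally, the 10.0-unit Stiffness threshold comes from a cited user guide; the step arithmetic shows what it means on this scale, not that another cut-off should replace it.

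**Conclusion.** The concern holds as a fault of presentation and reference, not of the model. From the SAP's own text and arithmetic, without assumptions: WOMAC response is improvement only, no matching worsened count is planned for WOMAC or SF-36, no reference rate exists in an uncontrolled study, and any one-category Stiffness improvement is a response. The size of the chance rate is conditional on the retest correlation, on SDs borrowed from the general population and on where baseline scores lie; over correlations from 0.5 to 0.95 the normal approximation spans 38% down to 4%. The endpoints are exploratory, the p-values nominal and the study unpowered, so what is at risk is the reading of the responder tables. No primary conclusion depends on it.

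**What to change.** In SAP 5.4.1, 5.5.1 and 8.8.2.1:

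- Classify each WOMAC and SF-36 scale at each visit as improved, unchanged or worsened, with the same threshold in both directions. Write out the SF-36 direction and inequality, and state whether any BPI responder is intended.
- Report all three classes at each visit, with the improved-minus-worsened difference and its 95% confidence interval at Weeks 24 and 72.
- State that the responder GEE is used only to estimate rates with confidence intervals. If a test is wanted, test improved against worsened.
- Footnote that a Stiffness response means any one-category change.

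The cost is SAP wording and small table changes, with no new data. The headline becomes net improvement, which is lower than the responder rate. The change also does not remove open-label expectation or regression to the mean; the latter matters most where SAP 8.8.2.5 splits SF-36 responders by baseline PCS, so that table should carry a caveat.
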